4.1 Eligibility

Community Intervention Group/Arm

Eligibility to participate in this community intervention will primarily be driven by location of residence and age, since screening CRC have established age criteria for screening initiation. A total of four community health navigators will be deployed in the South Shore community area. Each navigator will be trained to understand the eligibility criteria and determine subject eligibility. For those that consent to take the FIT kit and return it, the navigator will document the participants' eligibility in the appropriate REDCap participant information form (attached).

Standard of Care Comparison Group/Control Arm

Within the Mile Square Health Center system, lay navigators already work to do colorectal cancer screening in the Mile Square Health Center setting. It is standard of care for these navigators to engage patients in health education and awareness regarding the need for colorectal cancer screening. As such, each navigator is familiar with eligibility criteria for screening under standard of care. For the purposes of this study, we will use deidentified aggregate data from the CRC screening navigation program at the Mile Square Health Center in Englewood as a comparison group to evaluate the value of the community intervention relative to standard of care. As general practice, each navigator at MSHC keeps a running tally of the number of patients approached, deemed eligible, and who opt to participate in colorectal cancer screening during each day the navigator works in the health center setting.

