4.2 Inclusion Criteria

- Male or female adults ages 45 to 74, who speak English and reside in or near the South Shore community area or utilize

the Mile Square Englewood Health Center. Must not have had CRC screening in the previous 12 months.

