In addition to recruitment efforts in the barber shop and beauty salon, our community navigators who are trained on the study protocol will attend community events in the South Shore and surrounding communities such as the annual African Festival of The Arts (<https://www.aihua.org/african-festival-of-the-arts>) where UICC hosts an informational table each year. These navigators will use the attached CRC screening flyer, and engage with each potential participant to provide information and education about CRC screening using the attached script. If the participant is interested, the navigator will review the study information sheet and ask the participant to provide written consent to participate. Once the participant agrees to participate, the navigator will document the participant's contact information, and assist the participant in obtaining and understanding how to use and return their FIT. The navigator will also give the participant a short survey (attached) to complete. The FIT and survey will be returned to the UICC via mail or dropped off at the barber or hair salon using a drop box, where it will be processed following the manufacturer's instructions. Any positive FIT will be promptly reported (within 48 hours) to the MSHC clinical navigator, who will follow standard practices to register the participant as a patient, and navigate the participant through standard medical care if clinical follow-up is needed due to a positive screening and need for a diagnostic examination within the MSHC System. Participants who receive their FIT from a community navigator outside of the barber or hair salon setting will be offered a \$25 incentive (Walgreens store gift card or cash) to be paid upon receipt of the FIT to UICC. Each navigator will keep a tally of the number of participants who are approached, eligible, and who decline to participate in screening for evaluation purposes.

Standard of Care Comparison Group/Control Arm

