For the standard of care control arm, we will obtain deidentified aggregate data from the Mile Square Englewood patients that are approached following standard practice utilizing clinic schedules, walk-ins, etc. to identify potentially eligible participants for CRC screening during the intervention period. This aggregate data will include the number approached, the number eligible, the number that take and return the FIT kit, and the number of FITs returned. Among those that return the FIT, aggregate data will be provided detailing the proportion of positive FITs, the proportion of positive FIT participants who return for diagnostic services, and the proportion of detected cancers.

Table 2. Subject Enrollment Plan

Screening Target	Community-Based (Intervention Arm)
Colorectal	
 Community navigators will work with local businesses (barber shop, hair salon) to identify and screen eligible community members within or near the South Shore community area. The navigator will engage with each potential participant using the attached script. If the participant is interested, the navigator will document the participant's contact information, and assist the participant in obtaining and returning their FIT. Community navigators will attend community events to post the informational flyer and provide education about CRC to community members. At these events, they will identify and screen eligible community members within or near the South Shore community area. The navigator will engage with each potential participant using the attached script. If the participant is interested, the navigator will document the participant's contact information, and assist the participant in obtaining and returning their FIT.
Screening Target	
 Standard of Care Clinic-Based Comparision Group (Control Arm)

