FITs will be returned via mail directly to the UICC, where they will be processed following the manufacturer's guidelines. Navigators will call back each participant to let them know about the results of their FIT using the attached script. If a participant screens positive, the participant will be informed by the navigator, who will direct the participant to the MSHC- South Shore Clinic, and connect the participant to the MSHC- South Shore clinical patient navigator. We will track the time between FIT dispensing and return, and the time between FIT processing and participant agreement to engage in diagnostic testing with the clinical navigator at MSHC as indicated (for those that screen positive). Once the FIT is returned, participation in the study will end. However, for those that have a positive/abnormal FIT, the community navigator will refer the person to MSHC for clinical follow-up. This is not part of the research, but to ensure a continuum of care among those that screen positive. The clinical navigator will follow the standard clinical flow and standard clinical care practices used at the MSHC- South Shore Clinic to schedule the participant for a diagnostic test, and any further procedures or treatments necessary. This will include, but is not limited to, helping the participant enroll in a health insurance program if the participant is uninsured, and/or obtaining a voucher to pay for the diagnostic/further screening examinations and tests. For CRC screening, we have partnered with administrative and clinical staff at the MSHC- South Shore clinic in the South Shore community area to facilitate this transition when needed.

Standard of Care Comparison Group/Control Arm

For the standard of care control arm, the lay patient navigator at Mile Square Englewood Health Center will provide deidentified aggregate data from the Mile Square Englewood patients that are approached following standard practice utilizing clinic schedules, walk-ins, etc. to identify potentially eligible participants for CRC screening during the intervention period. This aggregate data will include the number approached, the number eligible, the number that take and return the FIT kit, and the number of FITs returned. Among those that return the FIT, aggregate data will be provided detailing the

proportion of positive FITs, the proportion of positive FIT participants who return for diagnostic services, and the proportion of detected cancer.

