8.1 Data Collection and Management Procedures

- Navigators will collect participant contact information for tracking and follow-up using REDCap.
- Survey data will be collected via a paper survey, which will be entered into REDCap. Following data entry, paper copies will be destroyed.
- All participant Protected Health Information (PHI), including contact

information, and full street address, unique participant ID numbers, demographic, the date a FIT was returned or diagnostic completed [colonoscopy]), navigation and follow-up data is stored on the University of UICC's password-protected secure server (K drive) in an encrypted Excel data entry workbook. Only the Principal Investigator (PI), Co-Investigators (Co-I), and key research personnel have access to the password-protected data entry workbook.

- Data will be harmonized and cleaned prior to analyses by the statistical team at the UICC and stored on the UICC secured server. All individual workstations at UIC that access data with PHI will be encrypted. PIs will have access to all data collected. Overall data management will be overseen by the PI and Research team.

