9.1 Data Analysis

- Prior to any analyses, all data sources (tracking, demographic, and questionnaire) will be cleaned and linked using the participant unique study identifier. We will summarize the data using frequencies and percentages for categorical variables, and means and standard deviations for continuous variables.

Aim 1: To assess the feasibility and efficacy of conducting a community-based CRC screening intervention in increasing CRC screening rates. We aim to evaluate the feasibility and efficacy of conducting a community-based navigation program for colorectal cancer screening. In both arms of the study, we will examine the number of participants who were provided with health education about colorectal cancer, the number of FITs distributed, and the number of FITs returned. We will summarize the number of persons screened positive and negative, and determine the proportion of positive screening participants who are referred to clinical care overall, and at the Mile Square South Shore and Englewood sites through our community navigation program (intervention) and existing MSHC lay clinical navigation program. We will compare the FIT return rate and average return time at the South Shore and Englewood sites to determine if the rates and times are similar. We will also determine return rates and times for participants who screen positive and are navigated to return the MSHC for diagnostic testing, and make comparisons across the intervention and control arms.

Aim 2: To evaluate individual-level knowledge related to CRC screening and risk factors. We aim to assess knowledge related to CRC screening and risk factors as measured by our short survey that participants will return with their FIT. We will summarize the frequency and percentage of respondents who have had a prior CRC screening, in addition to the frequency and percentage of respondents who select the correct answers on knowledge questions.

Aim 3: To characterize individual -level facilitators and barriers to engaging in CRC screening and related diagnostic tests and treatment when

applicable. We aim to evaluate facilitators and barriers people living in or near the South Shore communities experience related to CRC screening and related follow-up. We will summarize the respondent responses to survey questions about barriers and facilitators.

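### The between-arm comparison of diagnostic follow-up mixes attachment to MSHC, and possibly two different events, with completion of diagnostic work-up

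*Combined protocol and SAP*

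**What the plan says.** **Outcome.** Under Aim 1, section 9.1 states: "We will also determine return rates and times for participants who screen positive and are navigated to return the MSHC for diagnostic testing", and will "make comparisons across the intervention and control arms". It gives no denominator, time window, test, or rule for people worked up elsewhere.

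**Who is in each arm.** Section 4.1 says: "Eligibility to participate in this community intervention will primarily be driven by location of residence and age". Section 4.2 admits adults "who speak English and reside in or near the South Shore community area or utilize" the Englewood center, so MSHC use is an alternative route and not a requirement. After a positive FIT, section 5.0 passes the community participant to the MSHC clinical navigator, "who will follow standard practices to register the participant as a patient". The control arm consists of aggregate counts on Englewood patients, including "the proportion of positive FIT participants who return for diagnostic services, and the proportion of detected cancers".

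**Follow-up.** For the intervention arm, section 6.3 ends participation when the FIT is returned and says of the later referral: "This is not part of the research, but to ensure a continuum of care among those that screen positive". The same subsection tracks time from FIT processing until the participant agrees to diagnostic testing with the MSHC navigator. The control subsection tracks time until the participant engages in the testing itself.

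**Data held.** Section 8.1 stores "the date a FIT was returned or diagnostic completed [colonoscopy", without naming the source of the date. Section 11.0 keeps details of MSHC engagement for those who screen positive. Section 7.1 states that all diagnostic testing takes place within the MSHC system.

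**The concern.** An outcome tied to one provider is comparable between groups only if both are equally likely to use that provider. Here one group is approached in shops and at events and may have a doctor elsewhere; the other is approached at an MSHC clinic. If a South Shore participant takes a positive result to another provider, the plan has no means of knowing it.

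Two further problems compound this. The tracked events differ: agreeing to a test comes before having one and is easier to reach. And the outcome falls after the point at which section 6.3 says participation ends, so the status of these data as research data is unclear.

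Section 2.0 names lack of follow-up as one of the study's questions. A difference in the section 9.1 figures could be reported as better or worse follow-up when it reflects where people receive care, or which event was counted.

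**Working it through.** The plan states no rate, event count or effect size for this outcome, so there is no figure to reproduce. Every rate below is an assumption for illustration. Only the 600 enrolled (section 5.0) comes from the documents.

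**1. Effect of capturing MSHC work-up only.** Let c be true completion, equal in both arms, and s the share of completers worked up outside MSHC. If those people stay in the denominator as not followed up:

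- recorded rate = c × (1 − s)
- spurious difference (intervention − control) = c × (s control − s intervention)

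With c = 70%:

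| Outside share, intervention / control | Recorded, intervention | Recorded, control | Difference |
|---|---|---|---|
| 10% / 5% | 63.0% | 66.5% | −3.5 points |
| 20% / 5% | 56.0% | 66.5% | −10.5 points |
| 40% / 5% | 42.0% | 66.5% | −24.5 points |
| 10% / 10% | 63.0% | 63.0% | 0 |
| 10% / 20% | 63.0% | 56.0% | +7.0 points |

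The sign depends wholly on which arm has the larger outside share. The size does not shrink with more participants.

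**2. Effect of counting different events.** Section 6.3 states the mismatch for times. Suppose it carries over to the rates. Let 80% in each arm agree to testing and 70% of those complete it, so true completion is 0.80 × 0.70 = 56% in both arms. With outside shares of 20% and 5%:

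- intervention, agreement at MSHC: 0.80 × (1 − 0.20) = 64.0%
- control, completion at MSHC: 0.80 × 0.70 × (1 − 0.05) = 53.2%
- difference: +10.8 points

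With a 40% outside share in the intervention arm, its figure is 0.80 × 0.60 = 48.0% and the difference is −5.2 points. The two mechanisms pull in opposite directions, and either can dominate.

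**3. How many positives.** Expected positives = 600 × return rate × positivity.

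- Low: 600 × 0.30 × 0.03 = 5.4
- Middle: 600 × 0.60 × 0.05 = 18
- High: 600 × 0.90 × 0.08 = 43.2

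With 18 per arm (the control number is not stated) and rates near 70%, the 95% margin on a difference is 1.96 × √(2 × 0.70 × 0.30 / 18) = 0.30, or about ±30 points. Detecting 70% versus 56% with 80% power at two-sided 0.05 needs about 186 positives per arm; 18 per arm gives about 14% power.

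**The case against.** **MSHC may be the intended endpoint.** Section 2.0 names engagement within a healthcare system as a question alongside lack of follow-up, so return to MSHC can be a deliberate outcome. This stands, and is a reason to keep that outcome under its own name. It does not make it a measure of diagnostic completion.

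**The plan's premise is that testing happens at MSHC.** Section 7.1 says so, and section 6.3 offers help there with insurance and vouchers. But this is a statement of intent in the risk section. It gives no way of learning where a participant actually went.

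**Stronger readings are tempting but not supported.**
- A reader might infer that work-up elsewhere is counted as failure. Section 9.1 has no such coding rule; its wording can also mean that only those navigated to MSHC form the denominator. That reading does not measure completion among all positives either.
- A reader might infer that the comparison is biased against the intervention. The agreement/engagement mismatch can work the other way. Control patients may also go elsewhere, and Table 2 says the clinic navigators screen Englewood community members at events.
- A reader might infer that observation stops before the outcome. Sections 6.3, 8.1 and 11.0 all plan data after FIT return; the fault is a conflict in wording.
- A reader might infer that cancers are to be counted for Englewood only. Section 6.3 collects control diagnoses for comparison with the intervention arm, which implies a counterpart, although none is listed.

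**Few positives.** Sampling error would probably exceed most of these artefacts, and no test is named. This stands, and argues for descriptive reporting.

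**A call in one arm only** creates an ascertainment imbalance of its own. This also stands, and limits what may be compared.

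**Conclusion.** The concern holds in limited form. As written, the section 9.1 follow-up comparison cannot be interpreted as a difference in diagnostic completion: the outcome is tied to a provider to which the arms are differently attached, the tracked times end at different events, and section 6.3 conflicts with sections 8.1 and 9.1 on whether follow-up belongs to the research.

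That a larger share of South Shore participants would be worked up outside MSHC is plausible from how they are recruited, but no document gives a share for either arm. The illustrative differences therefore show only that the artefact could be material in either direction. The FIT return rate, the comparison at the center of section 3.0, is not affected. This is a cheap improvement to a further Aim 1 comparison, not a threat to the main result.

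**What to change.** **Section 6.3.** State that data collection for FIT-positive participants continues until the diagnostic test is completed or a fixed number of days after FIT processing, with matching consent wording.

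**Section 9.1.**
- Use one event in both arms (diagnostic test completed, not agreed to) and one denominator (all FIT-positive participants).
- In the intervention arm, record completion at MSHC or elsewhere through one call by the existing navigators. Show completion at MSHC separately, and report the number with unknown status.
- List intervention-arm diagnoses to match the Englewood aggregate in sections 5.0 and 6.3.
- Limit any between-arm comparison to completion at MSHC, labelled as engagement with MSHC. Unless Englewood can supply completion at any site, report that outcome descriptively per arm.

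**Reconcile** both arms' text in section 6.3 with sections 7.1, 8.1 and 9.1.

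**Cost.** Protocol and consent wording, plus one call to each FIT-positive participant (about 5 to 43 people under the assumed rates). Completion elsewhere would be self-reported, and the any-site result is likely to be descriptive only. The change concerns data collection and analysis; no change to clinical care is proposed.

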5.0 Subject Recruitment and Enrollment

Participants will have an opportunity to enroll in this project at multiple points as summarized in Table 2. We will enroll at least 600 men and women across a three-year period for CRC screening in the South Shore community area, and acquire deidentified aggregate comparison data for the men and women who engage in CRC screening in the Mile Square Englewood Health Center across the same three-year period.

Community Intervention Group/Arm

For the intervention arm, the team of community navigators will recruit participants from multiple venues. We will work with local business owners who are actively engaged in health advocacy and will use their local businesses as sites of participant recruitment (Cut It Out Curt, a barber shop and a hair salon (Location TBD)) to identify and inform eligible community members within or near the South Shore community area about CRC screening. These partners will post the attached CRC screening flyer, and engage with each potential participant to provide information and education about CRC screening using the attached script. If the participant is interested, the partner will inform one of our trained community navigators who will connect with the interested participant to review the study information sheet and ask the participant to provide written consent to participate. Once the participant agrees to participate, the navigator will document the participant's contact information, and assist the participant in obtaining and understanding how to use and return their FIT via mail. The navigator will also give the participant a short survey (attached) to complete. The FIT test, instructions, survey, and mailing envelope will be contained in a "FIT Kit," a labeled plastic bag, that will be

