6.1 Study Design and Procedures

6.2 Dimensions of the RE-AIM framework

The overall aim of this study is to assess the feasibility and efficacy of the community-based CRC screening intervention in increasing CRC screening rates. We have designed this controlled trial in an effort to improve the quality of CRC screening that people receive and to assess whether or not implementing a community-based intervention where FIT tests are dispensed by community stakeholder will increase screening rates for CRC in specific community areas in

Chicago. If we find evidence supporting the efficacy of our intervention, that will demonstrate that community-based CRC screening interventions that actively involve community stakeholders in screening education and implementation may be a potential tool to improve health outcomes among the people that live in medically underserved communities. The RE-AIM framework will be used to evaluate both process and outcomes of the intervention program (Gaglio et al. 2013; Glasgow et al. 1999; Glasgow et al. 2019). The RE-AIM framework has proven utility in assessing program impact. Through the RE-AIM Framework we will be able to assess Reach, Effectiveness, Adoption, Implementation and Maintenance.

Data will be collected to evaluate our ability to “reach” targeted community members, hard to reach community members and the targeted number of participants. This is defined as the absolute number, proportion, and representativeness of individuals who are willing to participate in screening within our target community area. The clinical outcomes proposed through this project include improved screening of high risk populations for CRC screening and improved early detection of cancer through improved screening. To disseminate the findings to key stakeholders and community members, we will hold town hall forums to inform community members of findings from the project and produce infographics that clearly and succinctly communicate study findings.

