12.1 Statistical Considerations

- The primary aim of this project is to evaluate the feasibility and efficacy of a community-based cancer screening intervention. The projected sample size will allow us to determine if the intervention is feasible, and we anticipate the sample size will be sufficient to make comparisons across the intervention and control arms of the study. The purpose of any analyses conducted is to understand the needs of the community being served and to inform future interventions in this area as they relate to cancer control and prevention.

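### Section 12.1 expects the sample to suffice for comparisons between arms, but nothing in the plan supports that for diagnostic follow-up among FIT-positive participants

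*Combined protocol and SAP*

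**What the plan says.** Section 5.0 sets the community-arm target: "We will enroll at least 600 men and women across a three-year period for CRC screening in the South Shore community area". For the control arm, over the same three years, the study will "acquire deidentified aggregate comparison data for the men and women who engage in CRC screening in the Mile Square Englewood Health Center"; no number is given.

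Section 3.0 names the FIT return rate as the effect under test. Section 9.1 begins its arm comparisons there: "We will compare the FIT return rate and average return time at the South Shore and Englewood sites". It then adds a second comparison, within a subset: "We will also determine return rates and times for participants who screen positive and are navigated to return the MSHC for diagnostic testing", again set against the control arm. No test, interval or expected count is attached to it.

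The only statement on sample size for comparisons is in section 12.1: "we anticipate the sample size will be sufficient to make comparisons across the intervention and control arms of the study". It is not restricted to FIT return.

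Section 6.2 lists among the clinical outcomes "improved early detection of cancer through improved screening". Section 9.1 contains no analysis of it.

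On follow-up itself, section 6.3 says of the community arm: "Once the FIT is returned, participation in the study will end". It places clinical follow-up after a positive test outside the research, yet also plans to time the interval from FIT processing to the participant's agreement to diagnostic testing. The control-arm text in the same section times to engagement in diagnostic testing. Section 8.1 stores the date a diagnostic procedure was completed, and section 11.0 provides for data on engagement with the health center.

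**The concern.** The number that matters for diagnostic follow-up is the number of positive tests. Each enrolee must return a kit and then test positive before contributing to this comparison, so its denominator is a small fraction of 600. A sufficiency statement that covers arm comparisons in general covers this one as well, and nothing in the plan shows that it can carry that weight.

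Two misreadings are at stake. A chance difference in follow-up could be reported as evidence that community navigation works. An absence of difference could be reported as showing that the two routes perform alike. Early detection rests on fewer events still. Separately, if follow-up is timed to agreement in one arm and to engagement in the other, the time comparison would set different events against each other at any sample size.

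**Working it through.** **Plan's own figure.** The minimum of 600 cannot be reproduced. The documents give no return rate, effect size, alpha, power or control-arm size, so there is no calculation to repeat.

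**Inputs.** From the documents: at least 600 enrolled in the community arm (section 5.0). Assumed, because the documents give no values: return 30% to 90%; positivity among returned kits 3% to 10%; follow-up of 50% in control against 70% in the community arm; two-sided alpha 0.05.

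**Step 1, expected positives** = 600 × return × positivity:
- 600 × 0.30 × 0.03 = 5.4
- 600 × 0.50 × 0.05 = 15
- 600 × 0.50 × 0.10 = 30
- 600 × 0.90 × 0.10 = 54

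**Step 2, power for 70% versus 50% follow-up.** Power = Φ[(d − 1.96·SE0)/SE1], where d = 0.20, SE0 uses the pooled proportion and SE1 the separate proportions.

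With 30 positives per arm: SE0 = √(0.6 × 0.4 × 2/30) = 0.1265; SE1 = √((0.25 + 0.21)/30) = 0.1238; (0.20 − 0.2479)/0.1238 = −0.39; power 35%.

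With 30 community positives and an unlimited control arm: SE0 = √(0.25/30) = 0.0913; SE1 = √(0.21/30) = 0.0837; (0.20 − 0.1789)/0.0837 = 0.25; power 60%.

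| Community-arm positives | Power, equal arms | Fisher exact, equal arms | Power, unlimited control | Exact 95% interval, observed rate near 50% |
|---|---|---|---|---|
| 15 | 19% | 10% | 33% | 27% to 79% (8/15) |
| 30 | 35% | 26% | 60% | 31% to 69% (15/30) |
| 54 | 57% | 49% | 86% | 36% to 64% (27/54) |

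With 5 positives per arm the same formula gives 9%; the normal approximation is rough there. At 80% power, 50% versus 70% needs 93 positives per arm.

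**Step 3, smallest difference from 50% detectable at 80% power.** Equal arms: about 44, 34 and 26 points at 15, 30 and 54 positives. Unlimited control: about 33, 25 and 19 points.

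**Step 4, cancers.** Expected number = positives × follow-up × yield. Assuming 50% to 100% follow-up and a yield of 2% to 10% among positives examined: 15 × 0.5 × 0.02 = 0.15 up to 15 × 1 × 0.10 = 1.5. With 54 positives, 54 × 0.5 × 0.02 = 0.54 up to 54 × 1 × 0.10 = 5.4. If 0.1% versus 0.3% of enrolees had a cancer detected, power at 600 per arm would be about 12%.

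**Step 5, contrast with FIT return.** For 50% versus 60% with 600 per arm: SE0 = √(0.55 × 0.45 × 2/600) = 0.0287; SE1 = √((0.25 + 0.24)/600) = 0.0286; (0.10 − 0.0563)/0.0286 = 1.53; power 94%. With 300 controls it is 81%.

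**Step 6, the event that is compared.** The follow-up event is agreement to testing (section 6.3, community arm), engagement in testing (section 6.3, control arm), completion of a procedure (section 8.1, stored date) or return for testing (section 9.1). Section 6.3 also ends participation before any of these occurs. The documents do not say which event section 9.1 uses in each arm.

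**The case against.** Section 12.1 states an expectation and ties it to no outcome. Read with section 3.0, it most naturally concerns FIT return, where Step 5 shows it is plausible. A reader might infer that the statement is wrong; the documents do not show that. What stands is that it is not limited to FIT return, while section 9.1 plans a further arm comparison for which no support is given.

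Every rate used here is an assumption, and 600 is a floor. The control arm could also be much larger than the community arm. At 54 positives an unlimited control arm lifts power for 50% versus 70% to 86%, and 50% versus 80% has 69% power at 30 per arm and 92% at 54. Even the extreme of 100% return and 15% positivity gives 600 × 1 × 0.15 = 90 positives, with 79% power for 50% versus 70% in equal arms. It would therefore go too far to call the comparison pure noise or to cap the expected cancers at two. At 15 or 30 positives, however, no control-arm size brings power for a 20-point difference to 80%.

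The plan is already largely descriptive: section 9.1 names no hypothesis test, and section 12.1 says the analyses serve to understand community needs and inform later interventions. That limits the harm, but the text still announces arm comparisons and an efficacy aim. A ban on any between-arm figure is not warranted; a difference shown with its interval is acceptable.

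A reader might also infer from section 6.3 that follow-up is not recorded. Sections 6.3, 8.1 and 11.0 do provide for tracking it, and the remark that it lies outside the research most likely refers to clinical care after referral. The conflict is one of wording and event definition. Likewise, no section lists cancer stage among the data, but the attached forms are not available, so it cannot be said that stage is never recorded.

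**Conclusion.** The point holds as a lack of support. Nothing in the plan shows the sample to be sufficient for comparing diagnostic follow-up between arms. Under the stated assumptions, the likely 5 to 54 community-arm positives would leave a moderate difference imprecisely estimated, unless return, positivity and control-arm size are all favourable. Early detection is listed as an outcome without a planned analysis, and few cancers are expected, so no comparison of it would be informative; removing that phrase alone is mainly editorial. The conflict over when participation ends and which follow-up event is timed needs no outside assumption. None of this calls for more enrolment or weakens the FIT return comparison on grounds of size.

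**What to change.** - **Section 12.1:** limit the sufficiency statement to the FIT return rate.
- **Section 9.1:** label diagnostic follow-up and detected cancers as descriptive. Report counts with denominators and exact 95% intervals in each arm. If a between-arm difference is shown, give its interval and state that it will not be read as evidence of efficacy or of similarity. Because control data are aggregate, agree with the clinic which counts and time summaries it can supply.
- **Section 6.2:** do not present improved early detection as an outcome that this study evaluates.
- **Sections 6.3, 8.1 and 9.1:** reconcile the end of participation at FIT return, and the placing of follow-up outside the research, with the planned analysis. Define one follow-up event and one time interval for both arms; the choice is the sponsor's.

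The cost is wording in these sections and a check with the clinic on event definitions. No further participants are needed. The downside is that the stated claims become less favourable.
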